## **10.2.2 Analysis of Long-Term Adverse Event Rates**

Long-term adverse event rates will be analyzed using event rates adjusted by cumulative exposure and will be based on the actual treatment received at the time of AE occurrence. Starting with Amendment 6, all subjects will receive open-label upadacitinib 15 mg QD, including those currently on upadacitinib 30 mg QD. For subjects who previously received upadacitinib 30 mg QD, adverse events and exposure to upadacitinib 30 mg QD will be censored at the time of dose switch; subsequent adverse events and exposure starting the day of first dose of upadacitinib 15 mg QD will be summarized under a separate group.

The detailed treatment groups, including the handling of dose switch, are defined in Section [8.1](#).

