1.1 Protocol Amendment: Summary of Changes

Previous Protocol Versions

Protocol	Date
Original	30 September 2015
Amendment 1	11 December 2015
Amendment 0.01 (Canada Only)	06 January 2016
Amendment 1.01 (Korea Only)	15 March 2016
Amendment 1.01.01 (Korea Only)	07 April 2016
Amendment 1.02 (France Only)	20 April 2016
Amendment 2	01 April 2016
Amendment 2.01 (Korea Only)	23 May 2016
Amendment 2.02 (Canada Only)	01 June 2016
Amendment 3	31 March 2017
Amendment 3.01 (France Only)	14 April 2017
Amendment 4	21 June 2017
Amendment 4.01 (France Only)	31 July 2017
Amendment 5.01 (France Only)	14 December 2017
Amendment 5.01.01 (France Only)	07 December 2018
Amendment 6	16 December 2019
Amendment 6.01 (VHP Countries, LT and GR)	06 March 2020
Amendment 7	15 July 2020

The purpose of this amendment is to:

- Apply administrative changes throughout the protocol.
Rationale: Revised text to improve consistency and readability, and/or provide clarification.
- Update Section 1.2, Synopsis
Rationale: Revised to be consistent with Amendment 8 revisions.
- Update Section 1.3, List of Abbreviations

Rationale: Updated to include new terms, Direct-to Patient (DTP) and Coronavirus Disease – 19 (COVID-19)

- Update Section 3.2, Benefits and Risks

Rationale: Revised to include the evaluation of the benefit and risk to subjects participating in the study relative to COVID-19.

- Update Section 5.1, Overall Study Design and Plan: Description

Rationale: Added provisions for virtual or alternative locations for study visits in the event of a pandemic situation like COVID-19 or any state of emergency (e.g., natural disaster, conflict/combat) to ensure the safety of subjects and site staff, while maintaining the integrity of the study.

- Update Section 5.2.3.2, Prohibited Therapy

Rationale: Revised Table 1 to update the list of examples of commonly used strong cytochrome 3A inducers.

- Update Section 5.3.1, Efficacy and Safety Measurements Assessed and Flow Chart

Rationale: Added clarifications on study activities that can be performed by phone/video conference or at local clinic/hospital/laboratory or through the optional home healthcare service in the event study visits are impacted by any state of emergency or pandemic situation like COVID-19 to ensure subjects' safety and study continuation, as permitted by IRB/IEC.

- Update Section 5.3.1.1, Study Procedures

- Outcomes and Questionnaires

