5.6 Discussion and Justification of Study Design

5.6.1 Discussion of Study Design and Choice of Control Groups

This study includes two periods.

Period 1 is a 12-week, randomized, double-blind, placebo-controlled period to compare safety and efficacy of upadacitinib versus placebo in subjects with moderately to severely active RA who are on a stable dose of csDMARDs and have an inadequate response to csDMARDs. Period 1 is designed to test superiority of upadacitinib versus placebo for achieving the primary endpoint (ACR20 for US/FDA regulatory purposes or LDA for EU/EMA regulatory purposes) at Week 12, and other secondary efficacy parameters, all on a stable background csDMARD therapy.

The purpose of Period 2 is to evaluate the long-term safety, tolerability, and efficacy of upadacitinib 30 mg QD and 15 mg QD in a blinded fashion in subjects with RA who have completed Period 1. Subjects who are assigned to upadacitinib treatment groups in Period 1 will continue to receive upadacitinib 15 mg QD or 30 mg QD per original randomization assignment in a blinded manner. Subjects who are assigned to placebo in Period 1 will be switched to receive upadacitinib 15 mg or 30 mg QD in a blinded fashion per pre-specified randomization assignments. Preventing dose reduction or escalation of upadacitinib during Period 2 will allow better assessments of long-term safety and efficacy of upadacitinib 15 mg QD versus 30 mg QD.

Starting with Amendment 6, all subjects will receive open-label upadacitinib 15 mg QD, including those currently on upadacitinib 30 mg QD.

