6.1.4 Adverse Event Collection Period

All AEs reported from the time of study drug administration until 30 days following discontinuation of study drug administration have elapsed will be collected, whether solicited or spontaneously reported by the subject. Subjects who discontinue study drug treatment but continue to participate in the study will have SAEs and non-serious AEs collected for the remainder of study participation. In addition, SAEs and protocol-related nonserious AEs will be collected from the time the subject signed the study-specific informed consent.

Adverse event information will be collected as shown in [Figure 4](#).

Figure 4. Adverse Event Collection

* Subjects who discontinue study drug but continue to participate in the study will have SAEs and Non serious AEs collected for the remainder of study participation.

Additionally, in order to assist the adjudication process, additional information on any potential cardiovascular events including thromboembolic events will be collected, if applicable.

In the case of any of the following reported events, an appropriate supplemental eCRF should be completed:

- Cardiac events;
- Myocardial infarction or unstable angina;
- Heart failure;
- Cerebral vascular accident and transient ischemic attack;
- Cardiovascular procedures (SAE Supplemental Procedure eCRF)
- Embolic and thrombotic events (non-cardiac, non-CNS).
- Hepatic;
- Renal;
- Herpes Zoster Infection;
- CPK increases considered by the investigator to be an AE;
- COVID-19

Supplemental study case report forms should be completed in the event of COVID-19 related missed/virtual visits, study drug interruptions or discontinuations, or adverse events (including documentation of specific signs/symptoms of infection and testing results).

COVID-19 infections should be captured as adverse events. If the event meets the criteria for a serious adverse event (SAE), then follow the SAE reporting directions per the protocol and above.

The following COVID-19 related supplemental eCRFs should be completed (for both serious and non-serious events):

- COVID-19 Supplemental Signs/ Symptoms

- COVID-19 Status Form

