## **8.0 Study Drug Exposure and Compliance**

### **8.1 Study Drug Exposure**

The duration of exposure to study drug will be summarized for the safety analysis set by the following groups.

1. Placebo

2. Upadacitinib 15 mg QD

This includes upadacitinib 15 mg QD exposure from subjects starting on upadacitinib 15 mg QD and subjects switching from placebo to upadacitinib 15 mg QD.

3. Upadacitinib 30 mg QD

This includes upadacitinib 30 mg QD exposure from subjects starting on upadacitinib 30 mg QD and subjects switching from placebo to upadacitinib 30 mg QD. Exposure is censored at time of dose switch from upadacitinib 30 mg QD to upadacitinib 15 mg QD.

4. upadacitinib 15 mg QD switched from upadacitinib 30 mg QD

This includes upadacitinib 15 mg QD exposure from subjects who switched dose from upadacitinib 30 mg QD to upadacitinib 15 mg QD.

Starting with Amendment 6, all subjects will receive open-label upadacitinib 15 mg QD, including those currently on upadacitinib 30 mg QD. Exposure to upadacitinib 30 mg QD (Group 3) will be censored prior to the day subject received the first dose of upadacitinib 15 mg QD, and subsequent exposure to upadacitinib 15 mg QD will be summarized under a separate group (Group 4).

The duration of exposure to study drug will be summarized for each group as specified above, with the number of subjects, mean, standard deviation, median, minimum and maximum values. In addition, the number and percentage of subjects exposed to study drug will be summarized for the following cumulative duration intervals.

- $\geq 2$  weeks
- $\geq 1$  month
- $\geq 3$  months
- $\geq 6$  months

- $\geq 9$  months
- $\geq 12$  months
- $\geq 18$  months
- $\geq 2$  years
- $\geq 2.5$  years
- $\geq 3$  years
- $\geq 4$  years

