### **4.0 Safety Analysis**

In listings of adverse events and deaths, a flag indicating whether the event or death was related to COVID-19 infection will be presented. A listing of COVID-19 related adverse events may be provided.

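### The long-term 15 mg and 30 mg adverse event rates cover different calendar time, so COVID-19 events weigh more on 15 mg, and no planned summary rate removes or aligns them

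*SAP*

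**What the plan says.** SAP 8.1 defines the groups used for long-term adverse event rates.

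- Group 2 (15 mg) holds "exposure from subjects starting on upadacitinib 15 mg QD and subjects switching from placebo to upadacitinib 15 mg QD". No stop at Amendment 6 is stated.
- Group 3 (30 mg) has one: "Exposure is censored at time of dose switch from upadacitinib 30 mg QD to upadacitinib 15 mg QD".
- Group 4 takes the 15 mg time of former 30 mg subjects and is kept apart from Group 2.

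SAP 10.2.2 applies the same rule to events: "adverse events and exposure to upadacitinib 30 mg QD will be censored at the time of dose switch". Under 10.2.2.1 each rate is all events divided by all exposure in the group, with no term for calendar period. The only long-term contrast is each dose minus combined placebo, for events of special interest.

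Protocol 1.1 dates Amendment 6 "16 December 2019", and SAP 7.0 notes that the switch visit varies by subject. SAP Appendix B 1.0 states that every subject was in Period 2 when the pandemic came. Protocol 6.1.4 says "COVID-19 infections should be captured as adverse events". For safety, Appendix B 4.0 provides that in the listings of adverse events and deaths "a flag indicating whether the event or death was related to COVID-19 infection will be presented", with an optional listing of COVID-19 events.

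Protocol 5.6.1 explains that holding the dose fixed in Period 2 "will allow better assessments of long-term safety and efficacy of upadacitinib 15 mg QD versus 30 mg QD".

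**The concern.** Group 3 time ends at about the point where pandemic time begins, while Group 2 time continues to Week 260. Dose and calendar period are therefore confounded in rates that will be printed side by side. A reader who compares serious infections, SAEs or deaths on 15 mg and 30 mg is partly comparing pandemic with pre-pandemic years.

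The same time carries a second imbalance. Protocol 5.5.5.1 ends the blind with Amendment 6, so Group 2 mixes blinded and open-label follow-up, while 30 mg follow-up precedes the open-label switch.

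At stake is the long-term dose comparison that Protocol 5.6.1 puts forward, and also the planned special-interest differences from placebo, since all placebo time is pre-pandemic. Long-term efficacy is not involved, because SAP 9.1.1 does not censor it at the switch.

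**Working it through.** The documents give no adverse event rate, patient-years (PY) or COVID-19 rate, so there is no plan figure to reproduce. What follows is an illustration.

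**From the documents:** 2:2:1:1 allocation of about 600, hence about 300 per active dose from Week 12; 260 weeks of treatment; Amendment 6 dated 16 December 2019; Period 1 reporting completed in 2017 (Appendix B 1.0).

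**Assumed:** uniform entry from 15 December 2015 to 1 December 2016 or 1 April 2017; pandemic from 1 March 2020; switch at the first 12-weekly visit 0, 90 or 180 days after the amendment date; discontinuation of 6% or 12% per year; no true dose effect.

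**Step 1: pandemic share of each group's exposure (simulated)**

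| Group | PY | Pandemic share |
|---|---|---|
| 2 (15 mg) | about 1,100–1,270 | 20–26% |
| 3 (30 mg) | about 830–1,075 | 0–9% |
| 4 (15 mg after 30 mg) | 150 or more | 93–100% |

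Two of the scenarios:
- Entry to April 2017, 90-day lag, 6% discontinuation: Group 2 is 331/1,269 = 26.1% and Group 3 is 37/976 = 3.8%.
- Entry to December 2016, 180-day lag, 12% discontinuation: Group 2 is 224/1,101 = 20.3% and Group 3 is 75/955 = 7.9%, a net share of about 12%.

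Across scenarios the net share (Group 2 minus Group 3) is about 12% to 26%.

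**Step 2: serious infections.** Relative excess ≈ COVID-19 rate × net share / base rate, with assumed base rates of 2.5–3.5 and COVID-19 serious-infection rates of 0.5–2 per 100 PY.
- Low: 0.5 × 0.12 / 3.5 = 0.06 / 3.5 = 1.7%.
- High: 2 × 0.26 / 2.5 = 0.52 / 2.5 = 20.8%.

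So the excess is about 2% to 21% with identical true rates on both doses.

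**Step 3: dose minus placebo, serious infections.** The COVID-19 component adds 0.5 × 0.20 = 0.10 to 2 × 0.26 = 0.52 per 100 PY to the 15 mg difference, and 0 to 2 × 0.09 = 0.18 to the 30 mg difference.

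**Step 4: all TEAEs.** For COVID-19 rates of 1, 3 and 10 per 100 pandemic PY, the 15 mg rate exceeds the 30 mg rate by 0.12–0.26, 0.37–0.78 and 1.25–2.6 per 100 PY.

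**Step 5: after the fix.** Removing COVID-19 events, or cutting both groups at the same point, brings the difference in this illustration to about 0.

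**Sensitivity to entry dates.** Entry from 1 June 2016 to 30 September 2017 raises the net share to 22–35% and the top of Step 2 to 2 × 0.35 / 2.5 = 28%. The last such entrant reaches Week 12 in late December 2017, which is hard to square with reporting completed in 2017, so this window is not used.

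**The case against.** The strongest reply is that COVID-19 is visible in the planned output. SAP 10.2.2.2 and 10.2.2.3 give rates by preferred term and group, with numerators and denominators, for TEAEs, SAEs, deaths and each event of special interest. A reader can find the COVID-19 terms and subtract them. This stands: it would be wrong to infer that COVID-19 is separated only in listings, or that a 30 mg excess in other infections would be hidden. But subtraction is left to the reader, the summary rates and placebo differences remain uncorrected, and exposure is still not aligned.

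Second, Group 4 keeps former 30 mg subjects' pandemic events out of Group 2 and gives a nearly contemporaneous 15 mg rate. True, but Group 2 itself is not cut, and Group 4 beside Group 3 is more confounded still.

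Third, no test or estimate of 15 mg against 30 mg is planned, and the Period 2 objective is to evaluate both doses. This limits the matter to descriptive rates. Late switchers also contribute some pandemic time on 30 mg, which the working allows for.

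Fourth, a reader might conclude that the long-term rates as a whole are biased against 15 mg. The documents do not support that. Late 15 mg time comes from subjects who tolerated years of treatment, and missed or virtual visits could lower detection of other events. Either could act in the opposite direction.

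**Conclusion.** The concern holds for the COVID-19 component of the long-term safety rates. That component raises 15 mg relative to 30 mg, and enters the 15 mg-minus-placebo differences more than the 30 mg ones. It affects only categories that can contain COVID-19 events: all TEAEs, SAEs, serious infections and deaths. The net direction over all adverse events is unknown.

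The 2% to 21% for serious infections is illustrative. It rests on assumed base and COVID-19 rates, entry dates, switch timing and dropout, none of which the documents supply. A larger figure is tempting: a completer entering on 1 April 2017 spends 831 of 1,820 days (46%) after the amendment date, and a 45% share would give 0.45 × 2 / 2.5 = 36%. That is one late entrant's share, not the group's. It ignores dropout, counts time before the pandemic and sets 30 mg pandemic time to zero.

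This is a modest but worthwhile improvement. The primary and Period 1 analyses are complete and unaffected, and SAP version 3.0 governs only future long-term reporting.

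**What to change.** Keep the planned full-exposure tables and add two.

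1. In SAP 10.2.2.1, 10.2.2.3 and Appendix B 4.0: TEAE, SAE, serious-infection and death rates per 100 PY excluding events flagged as COVID-19-related. The flag is already planned.
2. In SAP 10.2.2: a sensitivity table of Group 2 versus Group 3 rates, with Group 2 events and exposure cut at each subject's own first open-label dose under Amendment 6. The SAP does not define this date for 15 mg subjects, but Protocol 5.5.7 has the IRT record kit numbers and dispensing dates, so it should be derivable. If it is not, apply one common calendar date, such as 16 December 2019, to both groups. A site-level switch date is not a substitute, because the SAP describes the switch by subject and a site may have had no one on 30 mg.

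The cost is two extra tables. The second uses less 15 mg exposure and is therefore less precise, which is why it supplements the planned tables.

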### **10.2.2.1 Overview of Adverse Events Rates per 100 Patient-Years of Study Drug Exposure**

An overview of AEs per 100 patient-years of study exposure will be presented by treatment group and overall for the following AE categories.

- All TEAEs
- Treatment-emergent serious adverse events (SAEs)
- Treatment-emergent severe adverse events
- TEAEs reasonably possibly related to study drug
- TEAEs of special interest
- TEAEs leading to discontinuation of study drug
- TEAE leading to death

For this calculation, 1 year will be considered to be 365.25 days. For each treatment group, the numerator of the overall rate will be the total number of TEAEs reported for

the event; that is, a subject can contribute more than one event to the numerator. For each treatment group, the denominator of the rates will be the total number of days exposed to study drug summed across all treated subjects divided by 365.25. Please refer to Section 6.0 for the calculation of study drug exposure. The AE rate per 100 patient-years of exposure will be calculated as  $(\text{[numerator/denominator]}) \times 100$ . The number of AEs reported (numerator), the total number of years of study drug exposure (denominator), and the AE rate per 100 patient-years will be presented for each treatment group and overall.

In the AE overview summary, any event with an unknown severity will be considered as severe and any AE with an unknown relationship will be considered as having "reasonable possibility" of being related to study drug.

Additional AEs may be considered for tabulation/summary based on recommendations from Clinical and Safety as deemed appropriate.

For TEAEs of special interest, the point estimate and 95% CI (using normal approximation) will be provided for the treatment difference in AE rate per 100 patient-years between each upadacitinib dose group and the combined placebo group.

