6.1 Medical Complaints

The Investigator will monitor each subject for clinical and laboratory evidence of AEs on a routine basis throughout the study. The Investigator will assess and record any AE in detail including the date of onset, event diagnosis (if known) or sign/symptom, severity, time course (end date, ongoing, intermittent), relationship of the AE to study drug, and any action(s) taken. For SAEs considered as having "no reasonable possibility" of being associated with study drug, the Investigator will provide other cause(s) of the event. For AEs to be considered intermittent, the events must be of similar nature and severity. AEs, whether in response to a query, observed by site personnel, or reported spontaneously by the subject will be recorded.

All AEs will be followed to a satisfactory conclusion.

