6.1.1 Definitions

6.1.1.1 Adverse Event

An AE is defined as any untoward medical occurrence in a patient or clinical investigation subject administered a pharmaceutical product and which does not necessarily have a causal relationship with this treatment. An AE can therefore be any unfavorable and unintended sign (including an abnormal laboratory finding), symptom, or disease

temporally associated with the use of a medicinal (investigational) product, whether or not the event is considered causally related to the use of the product.

Such an event can result from use of the drug as stipulated in the protocol or labeling, as well as from accidental or intentional overdose, drug abuse, or drug withdrawal. Any worsening of a pre-existing condition or illness is considered an AE. Worsening in severity of a reported AE should be reported as a new AE. Laboratory abnormalities and changes in vital signs are considered to be AEs only if they result in discontinuation from the study, necessitate therapeutic medical intervention, and/or if the investigator considers them to be AEs.

An elective surgery/procedure scheduled to occur during the study will not be considered an AE if the surgery/procedure is being performed for a pre-existing condition and the surgery/procedure has been pre-planned prior to study entry. However, if the pre-existing condition deteriorates unexpectedly during the study (e.g., surgery performed earlier than planned), then the deterioration of the condition for which the elective surgery/procedure is being done will be considered an AE.

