8.1.5.2.1 Treatment-Emergent Adverse Events (TEAE)

AEs will be coded using MedDRA. A TEAE is defined as AE that began or worsened in severity after initiation of study drug.

AEs starting more than 30 days following the last dose of study drug will not be included in summaries of TEAEs. For subjects who continued into Period 2, AEs that are reported in Period 2 will be captured in the combined safety analysis of Period 1 and Period 2.

As a general safety summary, the number and percentage of subjects experiencing TEAEs will be summarized for each treatment group for the following AE categories:

- All AEs;
- All severe AEs;
- All reasonably possibly related AEs;
- All SAEs;
- Frequent AEs (reported in 2% of subjects or more in any treatment group);
- Frequent reasonably possibly related AEs (reported in 2% of subjects or more in any treatment group);
- Discontinuations due to AEs;
- Death.

Additional AEs may be considered for tabulation/summary based on recommendations from Clinical and Safety as deemed appropriate.

TEAEs will be summarized and presented by system organ classes (SOCs) and preferred terms (PTs) using MedDRA. The SOCs will be presented in alphabetical order, and the PTs will be presented in alphabetical order within each SOC.

TEAE will also be summarized by maximum severity and by maximum relationship.

The AEs of special interest (including but not limited to serious infection, opportunistic infection, herpes zoster, TB, gastrointestinal perforations, malignancies, MACE, renal dysfunction, anemia, increased CPK, non-cardiac, non-CNS embolic and thrombotic events, and drug-related hepatic disorders) will be summarized. Event rate (per 100 patient years) for AEs of special interest will also be summarized for the combined safety analysis of Period 1 and Period 2.

All AEs leading to discontinuation of study drug will be presented in listing format. A listing by treatment group of TEAEs grouped by SOC and MedDRA preferred term with subject identification numbers will be generated.

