#### **10.2.1.2 Adverse Events by System Organ Class and Preferred Term**

The number and percentage of subjects experiencing adverse events will be tabulated by SOC and MedDRA PT by "as treated" treatment group and overall. The SOCs will be presented in alphabetical order, and the PTs will be presented in alphabetical order within each SOC.

The following summaries of adverse events will be generated:

- All TEAEs
- Treatment-emergent serious adverse events (SAEs)
- Treatment-emergent severe adverse events
- TEAEs reasonably possibly related to study drug
- TEAEs leading to discontinuation of study drug
- TEAE leading to death
- Frequent AEs (reported in 2% of subjects or more in any treatment group)

Subjects reporting more than one adverse event for a given MedDRA preferred term will be counted only once for that term (most severe incident for the severity tables and most related incident for the relationship tables). Subjects reporting more than one type of adverse event within a SOC will be counted only once for that SOC. Subjects reporting more than one type of adverse event will be counted only once in the overall total.

As a sensitivity analysis, the AE summary by SOC and PT will be repeated by randomized treatment groups (upadacitinib 15 mg QD, upadacitinib 30 mg QD and the combined placebo groups). In this summary, all AEs with an onset date after the first dose of study drug will be included, regardless of whether the AE occurred more than 30 days after the last dose of study drug.

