### **10.2.2.3 Adverse Events of Special Interest Rates per 100 Patient-Years of Study Drug Exposure**

The Adverse Events of Special Interest (AESI) categories will be summarized and presented for each treatment group and overall using SOC and MedDRA PT. The AESI categories will be identified as defined in Table 8. Adjudicated cardiovascular events will be summarized and presented by treatment group using the CAC adjudicated categories.

For each treatment group, the Adverse Events of Special Interest (AESI) rate per 100 patient-years of exposure will be calculated overall, for each SOC and each PT, for each of the AESI listed in Section 10.2.1.6.

For this calculation, 1 year will be considered to be 365.25 days. For each treatment group, the numerator of the overall rate, the SOC rate, or the PT rate, will be the total number of TEAEs reported overall, for the SOC, or for the PT, respectively; that is a subject can be counted more than once overall, for a SOC, and for a PT. For each treatment group, the denominator of the rates will be the total number of days exposed to study drug summed across all treated subjects divided by 365.25. Please refer to Section 6.0 for the calculation of study drug exposure. The AE rate per 100 patient-years of exposure will be calculated as  $[(\text{numerator}/\text{denominator})]*100$ . The number of AEs

reported (numerator), the total number of years of study drug exposure (denominator), and the AE rate per 100 patient-years will be presented overall, for each SOC, and for each PT for each treatment group.

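### Long-term AE and AESI rates count event records only: SAP 10.2.2 gives no subject counts or first-event rate, and its one CI has no stated variance

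*SAP*

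**What the plan says.** **Numerator.** SAP 10.2.2.1 (overview), 10.2.2.2 (by SOC and PT) and 10.2.2.3 (AESIs) all use the total number of treatment-emergent AEs. In the overview, "a subject can contribute more than one event to the numerator". In the AESI section a "subject can be counted more than once overall, for a SOC, and for a PT", and 10.2.2.2 has the same rule.

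**Denominator.** In each section, "the denominator of the rates will be the total number of days exposed to study drug summed across all treated subjects divided by 365.25". Follow-up is not stopped at the first event.

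**Recording.** Protocol 6.1.1.1: "Worsening in severity of a reported AE should be reported as a new AE". Protocol 6.1: "For AEs to be considered intermittent, the events must be of similar nature and severity". Protocol 8.1.5.2.1: "A TEAE is defined as AE that began or worsened in severity after initiation of study drug". A worsened AE is thus a separate, treatment-emergent record.

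**Confidence interval.** SAP 10.2.2 plans one type. For AESIs, "the point estimate and 95% CI (using normal approximation) will be provided for the treatment difference in AE rate per 100 patient-years", each upadacitinib dose against placebo. No variance formula is given.

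**Counting subjects.** The count-once rule, "Subjects reporting more than one type of adverse event will be counted only once in the overall total", stands in SAP 10.2.1.2, which covers Period 1. Protocol 8.1.5.2 says its AE conventions hold, unless otherwise specified, for Period 1 and for both periods combined. Protocol 8.1.5.2.1 then asks for the number and percentage of subjects with TEAEs, and adds the AESI event rate for the combined analysis as a further summary.

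**The concern.** For most AESIs the safety question is how many subjects are affected per year of treatment. A record rate answers a different question, and the two separate when records cluster within subjects. Clustering can arise in two ways here.

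- **Splitting.** An episode that goes from mild to severe can enter the same PT numerator twice. Events are assigned by the treatment received when they occur (SAP 10.2.2), so an episode that worsens after the switch from 30 mg to 15 mg could add one record to each group.
- **Recurrence.** Protocol 6.1.7 allows re-challenge after a treated serious infection, leaves interruption for zoster to consideration, exempts NMSC from mandatory discontinuation, and lets subjects with symptom-free CPK rises continue at the investigator's discretion. Over up to 260 weeks a few subjects can supply many records.

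The long-term AE tables as specified would not show whether a high rate reflects many subjects or a few. The reader would also not know how the interval for the AESI difference from placebo was built, or whether it allows for repeat events in one subject.

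**Working it through.** The documents give no long-term event count, rate or CI width, so there is no planned figure to reproduce. The first step is a reading of the text; the rest are illustrations on assumed inputs. Steps 2 to 4 use a Poisson standard error for the intervals, which the SAP does not state.

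**1. Text.** Protocol 6.1.1.1 creates a new record on worsening. SAP 10.2.2.1 to 10.2.2.3 count every record, even within a PT, and no SAP rule joins records of one episode. Protocol 8.1.5.2 wants subject counts in the combined analysis. SAP 10.2.2.3 opens by saying that AESI categories will be summarised, but the only quantity it then defines is the event rate. The SAP does count subjects for long-term laboratory, liver and vital-sign findings (10.3.3.2, 10.3.3.3, 10.4.3), so the omission is specific to AEs.

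**2. Splitting.** Let a fraction f of episodes become two records. The mean number of records per episode is 1 + f, and the mean square is (1 − f) + 4f = 1 + 3f. The event rate is therefore 1 + f times the episode rate, the variance-to-mean ratio (VMR) is (1 + 3f)/(1 + f), and a nominal 95% interval covers 2Φ(1.96/√VMR) − 1.

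| f | Rate multiplier | VMR | Coverage |
|---|---|---|---|
| 5% | 1.05 | 1.10 | 93.9% |
| 10% | 1.10 | 1.18 | 92.9% |
| 20% | 1.20 | 1.33 | 91.0% |
| 30% | 1.30 | 1.46 | 89.5% |

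**3. Recurrence.** Assume 300 subjects followed for 3.3 years, a gamma frailty with variance 1, and no splitting. VMR is 1 + rate × 3.3. Simulated coverage of a single-group interval (4,000 runs):

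| Rate per 100 PY | VMR by formula | Coverage |
|---|---|---|
| 3 | 1 + 0.03 × 3.3 = 1.10 | about 94% |
| 10 | 1 + 0.10 × 3.3 = 1.33 | about 90% |
| 200 | 1 + 2.00 × 3.3 = 7.60 | about 53% |

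The effect is small for rare events and large for frequent ones. The SAP plans no long-term CI for the all-TEAE rate, so the last row shows how strong clustering could be; it does not describe a planned interval.

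**4. Sparse placebo data.** Group sizes and durations are in protocol 5.1 and SAP 4.2.

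- Placebo ceiling: 200 × 12 × 7/365.25 = 46.0 patient-years.
- 15 mg ceiling: (200 × 260 + 100 × 248) × 7/365.25 = 1,472 patient-years, assuming that nobody stops and leaving out subjects who switch from 30 mg.
- At an assumed 3 per 100 patient-years, placebo expects 46.0 × 0.03 = 1.4 events, and has none with probability exp(−1.38), about 25%.
- With no placebo events, the placebo term of the standard error is zero. With 29.7 events in 300 × 3.3 = 990 patient-years on active drug, the half-width is 1.96 × √29.7/990 = 0.0108 around a difference of 0.030. The interval runs from about 1.9 to 4.1 per 100 patient-years and excludes a true difference of zero.
- Simulated coverage of the difference interval at this rate is about 75% with independent events, and also about 75% with frailty variance 1. Sparse placebo data matter here; clustering adds almost nothing.

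**The case against.** **The event rate is in the protocol.** Protocol 8.1.5.2.1 names an event rate per 100 patient-years for AESIs, and events over exposure is a coherent quantity. Under the protocol's own definition a worsened AE is a new AE. This stands: the planned rate is not an error, and its excess over an episode rate is a difference between two measures. It does not explain why the rate stands alone.

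**The gravest AESIs leave little room for repeats.** MACE and thrombotic events come from the adjudication committee and gastrointestinal perforation from adjudication. Nothing shows that a worsening record creates a second adjudicated event. Confirmed DVT or PE, perforation, and malignancy other than NMSC or cervical carcinoma in situ require stopping study drug, and events more than 30 days after the last dose drop out. This also stands, and it limits the point to the event types named in the brief.

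**Subject-level information exists elsewhere.** SAP 10.1 lists subjects with TEAEs, 10.2.2.4 lists SAEs, deaths and discontinuation AEs, and 10.3.3.2 counts subjects with significant laboratory values, CPK included. These would let a reader trace a cluster. A listing is not a rate, though, and the laboratory tables do not cover zoster, NMSC or infections.

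**Readings that go too far.** A reader might infer that the planned CI assumes independent events. The SAP says only that a normal approximation is used, and only for AESI differences from placebo, so all that can be said is that the variance is unstated and within-subject correlation is not addressed. A reader might also infer that recording practice would make the two doses look different. SAP 10.2.2 plans no CI for 15 mg against 30 mg, and the documents give no reason for severity steps to be recorded differently by dose under blinding.

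**Conclusion.** The point holds as a gap in the long-term AE tables, worth closing because it is cheap. SAP 10.2.2 gives record rates only, leaves out the subject counts in protocol 8.1.5.2, and does not state the variance of its one CI. One episode can be counted more than once, and a few subjects can drive a rate. The documents do not establish that episodes will be double-counted to any given extent.

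The size is unknown. Splitting 10% of episodes would put the event rate 10% above the episode rate; that fraction, the frailty variance, the event rates and the 3.3 years of follow-up are all assumptions. For rare AESIs the stronger reason to specify the interval is the placebo exposure of at most about 46 patient-years, a ceiling that follows from the design. SAP 11.1 confines version 3.0 to future long-term reporting, so completed Period 1 results are unaffected.

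**What to change.** Keep the event rate and amend SAP 10.2.2 as follows.

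1. Add, for each AE category and AESI, the number and percentage of subjects with at least one event, by the treatment groups of SAP 8.1.
2. Add the exposure-adjusted incidence rate: subjects with an event divided by person-time to first event or end of exposure. A second record in the same subject and category adds nothing to this numerator, so splitting and recurrence no longer affect it. State whether a subject with an event before a treatment switch is at risk again in the new group.
3. Base the AESI comparison of each dose with placebo on the first-event rate, with an interval that behaves with few or no placebo events, such as an exact or score-type interval.
4. If CIs for event rates are kept, use a robust or negative binomial variance and say so.

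Joining records opened only because severity worsened is optional, since the documents describe no way to identify them.

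The cost is SAP wording, one extra set of tables, and two rate types to explain. No new data are needed. The first-event rate does not remove the contrast between 12 weeks of placebo and up to 260 weeks of active treatment, which still needs a caveat beside the comparison.
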